# 3.2.3 Primary Outcome and Analysis

• **Justification of primary outcome variable: MDS-UPDRS** – Although the original UPDRS was employed in our phase 2 study of urate elevation as well as the key observational studies

(DATATOP and PRECEPT) linking urate to slower PD progression, features of the revised MDS version warrant its use in place of the original as our primary variable of clinical PD status:

- The MDS-UPDRS was developed to improve upon the original UPDRS by better assessing the more recently appreciated breadth of non-motor features. (See Sec. 6.2.1 for scale overview.)
- o Responsive to NIH guidance and to increased appreciation of the value of incorporating patient-reported outcomes (PROs) to enhance the relevance and validity of study results, approximately 40% of its items constitute PROs (vs. none in the original UPDRS).
- o Importantly for our phase 3 trial, although the MDS-UPDRS is closely modeled on and highly correlated with the original UPDRS, it appears to have greater sensitivity for monitoring clinical progression compared to original UPDRS. 145
- o The MDS-UPDRS has been validated across its multiple motor and non-motor domains, and across cultures in independent studies. 138,151,152
- Availability of standardized training and certification 153 facilitates quality and consistency of its administration. Training resources are accessible for both in-person and online training/reinforcement.
- o Increasingly adopted for use in PD clinical research, including as primary endpoint for trials designed to evaluate long-term disease-modification as well as for symptomatic effects. The MDS-UPDRS is now recommended (along with the original UPDRS) as a core instrument among NINDS common data elements (CDEs) for PD studies.
- Justification of primary analysis: difference in change in MDS-UPDRS over 2 years -Neuroprotective candidates with dopaminergic properties, even those with only mildly
  symptomatic antiparkinsonian effects (e.g., selegeline, rasagiline), have proven challenging to
  assess for their disease-modifying potential. As a result more complex (e.g., delayed-start) study
  designs have been pursued in attempts to tease apart symptomatic and neuroprotective effects. 156159 However, the complexities of these designs then created their own challenges of
  interpretation. 160 By contrast, for candidate protectants lacking symptomatic efficacy the most
  rational phase 3 efficacy designs may rely on a simpler structure of parallel groups assessed using
  a 'change in a rating scale over time'. 154 Thus while decidedly problematic in the study of a
  symptomatic agents for their influence on long-term clinical course, this parallel group design
  remains the historically best studied and most common 'neuroprotection' trial design in PD. 156, 157
  It is well suited to putative protectants like inosine that are unlikely to acutely impact
  dopaminergic neurotransmission or parkinsonian symptoms.

Accordingly, changes in scores on an appropriate clinical rating scale – the MDS-UPDRS as justified above—will be compared between early PD subjects randomized to placebo or urate-elevating inosine treatment over a 24 month period for the primary efficacy analysis of the trial. The design and primary analysis are further supported by:

- Evidence of non-futility of inosine (and possible efficacy in subgroup analyses) using change in UPDRS scores from the preceding phase 2 experience in the SURE-PD study. (See Sec. 2.2.3). A recently proposed 'road map' to clinical development of candidate disease-modifying agents highlights the efficiency of sequential investigations and the value of advancing to fuller efficacy trials with an outcome analysis similar to that used in demonstrating non-futility.
- Observational data from the DATATOP and PRECEPT trial cohorts linking higher urate with favorable rates of progression assessed as difference in UPDRS change over two years, approximating the planned primary efficacy analysis. Although higher urate

was also a significant predictor of delayed disability (warranting dopaminergic medication) in these cohorts, comparing MDS-UPDRS change has advantages as our primary outcome variable. Change in a continuous variable over time can offer greater statistical power over that achieved with a dichotomous endpoint like disability warranting dopaminergic therapy. Differences in proportions reaching this disability milestone will included among secondary analyses of the trial.

- O Recent/current use of this parallel group design with change in UPDRS over time in the primary efficacy analysis in the QE3, FS-ZONE and STEADY-PD III trials of non-dopaminergic agents (coenzyme Q10, pioglitazone and isradipine) posited to have disease-modifying properties.
- Wash-out period option for confirming lack of symptomatic efficacy, though not part of the primary analysis, may strengthen the evidence against an acute antiparkinsonian action of inosine. In the SURE-PD trial no effect of urate-elevating inosine treatment was apparent during the 3-month treatment initiation period or conversely during the 1-month wash-out. If a lack of symptomatic efficacy were replicated using MDS-UPDRS with the greater sample size of the phase 3 trial, then a positive result of divergent rates of change over two years in the primary analysis would be more suggestive of a disease-modifying benefit of urate-elevating inosine treatment. However, even under this scenario in the absence of a commensurate effect on an associated meaningful biomarker of PD progression the results would not suffice to prove slowing of the disease. An indication for disease modification would thus likely require additional clinical investigation.

## 3.2.4 Additional Key Safety Features

#### 3.2.4.1 Pre-Study Determinations of Food and Drug Interaction

In order to further reduce the variability in inosine bioavailability and urate elevation, and the associated AE risk, standard drug-drug and drug-food interaction studies (per FDA guidance) will be completed in advance of the trial. Evidence for substantial interactions will prompt modified dosing instructions limiting concomitant dosing with specified medication and/or requiring subjects to take study drug on an empty stomach (or consistently with or without food).

# 3.2.4.2 Modification of Uric Acid Stone Risk Factor Management Plan

The likelihood of gouty arthritis and uric acid urolithiasis – the two major known side effects of hyperuricemia –increase with age. $^{64,89,164-166}$  Accordingly, these are the main inosine-induced AEs anticipated in this study of early PD patients, who are expected to be over 60 years of age on average. $^{30,31}$  To help avoid them, any history of gout or uric acid urolithiasis will remain an eligibility exclusion criterion, as will a screening urine test result showing low pH ( $\leq$ 5.0), a major risk factor for uric acid urolithiasis. $^{29,64,87,88}$ 

Although no cases of gouty arthritis developed during SURE-PD, three subjects developed urolithiasis on inosine treatment and uric acid composition was documented in one.  Because urine pH can be readily identified and raised with common oral alkalinization treatments the phase 3 trial will employ additional measures to monitor for uric acid urolithiasis risk and a lower threshold for initiating standard alkalinization therapy. Based on SURE-PD data linking the presence of uric acid crystalluria (UAC) and low urine pH to the subsequent development of uric acid stones, urine samples provided at each visit will be processed centrally for blinded UAC determinations as well as pH measurements. These data will be followed and alkalinization will be triggered by persistently acidic urine (PAU) with or without the presence of UAC as follows (detailed in Sec. 8.4):

- Urine pH  $\leq$ 5.0 in 2 consecutive samples
- Urine pH ≤5.5 in ~3 consecutive samples (or fewer in the placebo group as needed to maintain a similar likelihood of alkalinization in the placebo and inosine groups; see Sec. 8.4.2)
- Uric acid crystalluria + urine pH  $\leq$  5.5 in 1 of the last 2 samples

Alkalinization therapy will be continued, advanced or reduced based on an algorithm that considers urine pH and crystalluria responses. Subjects on alkalinization therapy will also be carefully monitored for any adverse effects of alkalinization. Although asymptomatic renal stones can be detected by ultrasonography, its sensitivity is relatively low and is considered an appropriate monitoring test only when urine pH is below 5.5 in those who are otherwise at high risk of uric acid urolithiasis. Computerized tomography scans have the greatest sensitivity for uric acid renal stones (which are not radioopaque on plain films), but drawbacks including the serial low level radiation exposure that would be required for monitoring offset any diagnostic benefit in the present study. All subjects will also be counseled on avoiding dehydration, an avoidable and remediable risk factor for both gout and urolithiasis.

By reducing the number of UA urolithiasis AEs, these bolstered prevention measures will help minimize unblinding. Similarly, knowledge gained from experience with inosine in phase 2 will reduce unblinding as we have observed that stones can form on placebo, do not necessarily contain UA, and would normally be managed without disclosure of treatment assignment (see Sec. 8.8).

# 3.2.4.3 Reducing Risk of Possible Cardiovascular Adverse Effects

Also of particular relevance to the PD population is the risk of cardiovascular disease (CVD), which is an important even if uncertain risk of higher urate levels, as detailed above. Individuals with higher serum urate have a significantly increased risk of hypertension, coronary heart disease, and stroke. Although these associations may in part be confounded by obesity and other risk factors, 98,105 potential for a long-term neuroprotective effect of urate or its precursors must be weighed against potential adverse cardiovascular effects. It is worth noting that amongst PD patients in developed countries CVD is common and indeed is a leading cause of death. Moreover, CVD and its major sequelae of myocardial and cerebral infarction are far less reversible than urate-related crystal disease. On the other hand, recent data from a small study of urate-elevating inosine in MS and from the SURE-PD trial showed no evidence of blood pressure elevation compared to placebo despite months to years of substantial elevation of serum urate levels.

The main approach to reducing possible CVD risk during the SURE-PD trial was through the exclusion of those with a significant history (Sec. 4.2), particularly prior myocardial infarction or stroke and heart failure with an ejection fraction <45%. The lack of evidence for inosine-associated CVD events in the SURE-PD trial reflects a sample size and follow-up period that are too small to offer substantial reassurance. Accordingly, these exclusion criteria will remain unaltered in the phase 3 trial. Assessments for development of CVD during the trial will include frequent review of all AEs, and regular blood pressure and electrocardiographic monitoring.

Although serum urate has also been linked to metabolic syndrome and diabetes,  which is itself a major risk factor for CVD, SURE-PD data  showed no effect of long-term urate-elevating inosine treatment on body weight or blood sugar. In any event, risk of type II diabetes-related CVD will also be reduced through exclusion of those with evidence of CVD.

## 3.3 Study Duration and Periods

The total time of active participation in the study (including screening, treatment and wash-out periods) is 2.25 years for each subject completing the study (see Schedule of Activities; Sec. 7.7), and includes:

- Screening of up to 60 days from Screening Visit 1 (SC1) to enrollment at Baseline Visit. Because of the substantial (~50%) chance that the results of serum urate screening test will be exclusionary (Fig. 9, Sec. 3.1), the screening process at PSG sites is split into two visits with testing on a brief initial visit (SC1) primarily limited to the serum urate measurement. For those subjects who pass SC1, most of the remaining screening procedures are conducted on a longer second screening visit (SC2) and if still eligible then a subsequent DAT brain scan at a local neuroimaging center.
- Treatment (Period 1) of 720 ± 7 days (~24 months) approximates the 2-year observation periods of the DATATOP, PRECEPT and SURE-PD studies, on which the present trial is modeled. Extending follow-up beyond 24 months would provide diminishing returns as the primary outcome variable of MDS-UPDRS score is censored from the primary analysis after initiation of symptomatic antiparkinsonian therapy, which is expected to have occurred in the majority (two thirds) of placebo subjects by that point. Randomized, placebo-controlled, double-blind treatment is initiated at the baseline visit (BL) and gradually advanced and titrated up to a maximum 6 capsules/day or until the target serum urate range of 7.1-8.0 mg/dL is reached in the inosine-treated group. After wash-in/titration visits (V01, V02) at 3 and 6 weeks after BL, scheduled visits (V03 V10) will occur at 3-month intervals for clinical and safety assessments, including a serum urate measurement for any algorithmic dosage adjustments needed to maintain levels within the 7.1-8.0 mg/dL target range for those in the inosine group. Mirrored adjustment in the number of placebo capsules/day help ensure subject and site staff remain blind to treatment assignment.
- Wash-out (Period 2) of 90 ± 7 days, ending ~27 months after enrollment. Three monthly evaluations will be conducted after discontinuation of study drug at V10 (after 24 months of treatment), two by phone (TE1 and TE2 at months 25 and 26, respectively) and the final visit (SV) in person at month 27. The multiple visits will allow for serial assessments of the need for dopaminergic therapy during and after the reversal of any short-term effect of inosine or its withdrawal, as well as for any late adverse effects of the treatment or its withdrawal.

# 4 SELECTION AND ENROLLMENT OF SUBJECTS

After screening approximately 667 consented subjects, ~270 women and men (age 30 or older) with early idiopathic PD are expected to enroll at approximately 60 PSG study sites (see Fig. 9 in Sec. 3). At the time subjects undergo randomization they will have not yet developed sufficient disability to require treatment with dopaminergic agents other than MAO-B inhibitors, and they will not appear likely to develop it imminently (i.e., within 3 months).

Subjects withdrawn from the study will not be replaced.

#### 4.1 Inclusion Criteria

Study subjects meeting all of the following criteria will be allowed to enroll in the study:

- 1. Willingness and ability to give written informed consent and to comply with trial procedures.
- 2. Fulfillment of diagnostic criteria for idiopathic PD with at least two of the cardinal signs of PD (resting tremor, bradykinesia, rigidity) present at 2nd screening and baseline evaluations, as assessed by the Site Investigator.
- 3. Absence of current or imminent (within 90 days of enrollment) PD disability requiring dopaminergic therapy, as assessed by the Site Investigator.
- 4. Modified Hoehn and Yahr Scale Stage 1 to 2.5 inclusive.

- 5. Age 30 or older at the time of PD diagnosis.
- 6. Diagnosis of PD made within 3 years prior to 1st Screening Visit.
- 7. Non-fasting serum urate  $\leq 5.7$  mg/dL at 1st Screening Visit (SC1).
- 8. If the subject is female, then:
  - a) Being surgically sterile (hysterectomy or tubal ligation), or
  - b) Being postmenopausal (last menstruation was two years or more prior to 2nd Screening Visit), or
  - c) For those of childbearing potential
    - Using a reliable form of contraception for 60 days or more prior to Baseline Visit and agreeing to continue such use for 30 days post last dose of study drug. Reliable forms of contraception include: abstinence; implanted, injected or oral contraceptives (birth control pills), intrauterine device in place for at least 3 months prior to Baseline Visit, vaginal ring with spermicide, barrier with spermicide such as male or female condom, diaphragm or cervical cap, transdermal patch; male partner with vasectomy.
    - And having a negative pregnancy test at the 2nd Screening Visit. [Note that a urine pregnancy test will be performed at screening on all women who are not at least two years postmenopausal or surgically sterile.]

#### 4.2 Exclusion Criteria

Study subjects meeting any of the following criteria during screening evaluations will be excluded from entry into the study:

- 1. Atypical parkinsonism, including that due to drugs, metabolic disorders, encephalitis, cerebrovascular disease, normal pressure hydrocephalus, or other neurodegenerative disease.
- 2. Dopamine transporter brain scan without evidence of dopamine deficit.
- 3. History of gout.
- 4. History of uric acid or urate urolithiasis, or recurrent urolithiasis all of unknown type.
- 5. A screening test positive for uric acid crystalluria, urine pH  $\leq$  5.0, or an estimated glomerular filtration rate (GFR) < 60 ml/min/1.73 m^2.
- 6. History of myocardial infarction or stroke.
- 7. Symptomatic congestive heart failure with a documented ejection fraction below 45%.
- 8. History of severe chronic obstructive pulmonary disease.
- 9. History of nephrectomy.
- 10. Mini Mental State Exam score < 25; i.e., a score of 0 to 24.
- 11. Use of any anti-parkinsonian medication (including levodopa, dopamine agonists, amantadine, entacapone and the anticholinergic agents trihexyphenidyl and benztropine) other than monoamine oxidase-B inhibitors within 60 days of Baseline, or in excess of 90 days.
- 12. Change in the dosage of (or initiation of) a monoamine oxidase-B inhibitor within 90 days prior to Baseline, i.e., entry on a MAO-B inhibitor requires a stable dosage for the 90 days prior to Baseline.

- 13. Use of the following within 30 days prior to the Baseline Visit: inosine, allopurinol, febuxostat, probenecid, more than 50 IU of vitamin E daily, or more than 300 mg of vitamin C daily (though a daily standard multivitamin such as Bayer One-A-Day® or Centrum® is permissible), reserpine, methylphenidate, amphetamines, cinnarizine, monoamine oxidase-A inhibitors, tetrabenazine, neuroleptics or other dopamine blocking drugs.
- 14. Use of the following within 90 days prior to the DAT neuroimaging screening evaluation: modafinil, armodafinil, metoclopramide, alpha-methyldopa, methylphenidate, reserpine, or amphetamine derivative.
- 15. Unstable dosing of a thiazide -- such as hydrochlorothiazide (e.g., Esidrex), chlorothiazide (e.g., Diuril), chlorthalidone (e.g., Hygroton), indapamide (e.g., Lozol), metolazone (e.g., Zaroxolyn), which are permissible as long as the subject is on a stable dose from 1 week prior to the 1st Screening Visit through the Baseline Visit.
- 16. Known unstable medical or psychiatric condition that may compromise participation in the study. (Note that difficulty swallowing large capsules might preclude participation due to the size of the study drug capsules.)
- 17. Clinically serious abnormality in the screening visit laboratory studies or ECG, as determined by the Site Investigator.
- 18. Participation in another investigational treatment study within 30 days prior to the Baseline Visit.
- 19. Known hypersensitivity or intolerability to inosine.
- 20. Known hypersensitivity to DaTscanTM (either to the active substance of I-ioflupane or any of the excipients).

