#### 3.2.1.2 Lower Serum Urate

A unique additional defining feature of the targeted PD population is its lower serum urate levels (≤5.7 mg/dL on initial screening). This subset of early PD patients is rationally selected for urate elevation for several reasons.

- First, for safety we considered elevating serum urate among those already in the upper range of normal at 7-8 mg/dL to clearly hyperuricemic levels above 8 mg/dL to pose an unnecessary risk to those subjects, especially because we are relying epidemiological and clinical studies with very few data for subjects above 8 mg/dL.
- Second, those with lower serum urate are enriched for faster progressors (by definition of the relation between urate and progression), and thus may have more to gain from putative disease modifying benefit.
- Third, the non-linear shape of the curve describing the urate-progression (see Fig. 3A above) and the urate-PD risk relationships further supports the rationale for enrolling all those below the 5.8 mg/dL (near the boundary between the 3rd and 4th quintiles in Fig. 3A). Because the risk of progression remains relatively high and unchanging (flat) across the lowest 3 quintiles for serum urate before dropping down more sharply to lower risks in the two highest quintiles (with the highest corresponding to ~7-8 mg/dL) it suggests that all in the selected subpopulation could gain a similarly full benefit of urate elevation to 7-8 mg/dL -- regardless of whether one starts at 3.5 mg/dL (lowest quintile) or 5.5 mg/dL (middle quintile).

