## 7.1.3 Screening Visit Two (SC2)

SC2 must occur after SC1 and before the DS1 visit. Subjects are to proceed to SC2 only if they met preliminary eligibility at SC1, including serum urate level.

The following procedures and evaluations are to be performed at SC2:

- Review assessable inclusion/exclusion criteria
- Obtain medical history
- Review and document concomitant medications
- Assess and document adverse events/experiences (AEs)
- Conduct neurological exam
- Conduct physical exam
- Assess PD features
- Administer MDS-UPDRS Parts IA and III
- Provide MDS-UPDRS Parts IB and II and Neuro-QOL to subject for self-administration
- Assess Modified Hoehn and Yahr Scale
- Administer Mini-Mental State Exam (MMSE)
- Obtain weight and orthostatic vital signs (supine and standing blood pressure and heart rate refer to operations manual for standardized procedure)
- Conduct 12-Lead Electrocardiogram (ECG)
- Obtain blood for safety lab tests: serum urate and chem 7 panel
- Obtain urine for pregnancy test for all women unless they are at least two years postmenopausal, or surgically sterile
- For an interested, eligible subject obtain written informed consent for the optional Smart4SURE substudy
- Assist a consented Smart4SURE substudy subject in downloading and registering the Smart4SURE app on the subject's smartphone, and conduct an online training session via the app (Please note: If necessary, consent and training for the Smart4SURE substudy can take place at an additional visit to the study site after SC2).
- Distribute container for 24-hour urine collection at home and instruct subject in collection/storage procedures

- Schedule time to contact subject after SC2 serum urate and other lab and ECG results have been received
- Tentatively schedule DAT scan and Baseline Visit (with at least 5 business days between them)

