## 7.2.2 Post Study Visit Telephone Calls

Beginning with the Baseline Visit, serum urate test results will not be provided to sites. Instead the serum urate result will only be provided to an unblinded DCC Programmer and used in an algorithm to determine if a subject's study drug should be increased, decreased, or remain steady. (See Sec. 5.1.2.3)

If serum urate level warrants altering capsule dosing, the DCC will notify both the Site Investigator and Coordinator by email within 3 days of the visit. The Site Investigator or Coordinator should immediately notify the subject and update the Dose Management Log. Dosage increases, reductions, or holds should be initiated as soon as the subject is notified.

If the most recent urine pH/sediment results trigger the initiation or change of alkalinization therapy, then the Site Investigator or Coordinator should immediately notify the subject on how to begin or modify use of potassium citrate (or an alternative alkalinizing agent) according to the alkalinization algorithm in Sec. 8.4.2.

A follow-up phone call will take place after each study visit once the site is informed of a dosage change. The following will be performed and documented during the call:

• Inform the subject to either increase, reduce or hold their study drug

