6.2 Analysis Samples

The following analysis samples will be used for testing effectiveness, efficacy, safety, and tolerability endpoints:

- Intent-to-treat (ITT) Sample: Participants who are randomized, classified according to their randomized treatment assignment. Participants determined to have been ineligible prior to randomization, participants who never initiate study drug, and observations made after premature permanent discontinuation of study drug are included in this sample.
- As-treated (AT) Sample: Participants who are eligible, randomized, and take at least one dose of study drug. If a participant permanently discontinues study drug, observations made during period 1 will be censored following the first visit after study drug discontinuation. Separate analyses will classify participants in the AT sample either according to the actual treatment received or according to the average post-baseline serum urate concentration achieved. Participants randomized to inosine who report not taking inosine will be reclassified as placebo participants. Participants randomized to placebo who report taking inosine or whose serum urate during treatment averages 6.5 mg/dL or greater will be reclassified as inosine participants.

• Safety and Tolerability (ST) Sample: Participants who are randomized and take at least one dose of study drug, classified according to the actual treatment received. Participants determined to have been ineligible prior to randomization and observations made after premature permanent discontinuation of study drug are included in this sample.

The primary efficacy analyses will use the ITT sample to best estimate the expected effectiveness of urate-elevating oral inosine supplementation in clinical practice, recognizing that compliance in clinical use may differ from compliance in the clinical trial. Secondary analyses of efficacy outcomes will use the AT sample to best estimate efficacy of inosine supplementation as administered and serum urate elevation as achieved. Analyses of safety and tolerance will use the ST sample.

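### The look-back for urate-lowering drugs is counted from Baseline, but the qualifying urate is drawn at SC1, up to 60 days earlier, so a drug-lowered value can satisfy the entry criterion

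*Protocol*

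**What the plan says.** - **Urate limit.** Inclusion criterion 7 (Protocol 4.1) requires a urate of 5.7 mg/dL or less at SC1. Protocol 7.1.3 makes this the gate to the next visit: "Subjects are to proceed to SC2 only if they met preliminary eligibility at SC1, including serum urate level". Urate is measured again at SC2 and Baseline, but no limit is attached to either.
- **Timing.** Protocol 3.3 allows "Screening of up to 60 days from Screening Visit 1 (SC1) to enrollment at Baseline Visit". The Schedule of Activities (7.7) gives SC1 a window of day -60 to -13 and SC2 a window of day -58 to -11.
- **Drug look-back.** Criterion 13 excludes "Use of the following within 30 days prior to the Baseline Visit: inosine, allopurinol, febuxostat, probenecid", along with certain vitamins and dopamine-blocking and other drugs.
- **Neighbouring criteria.** Criterion 14 counts its window back from the DAT scan. Criterion 15 names thiazides, "which are permissible as long as the subject is on a stable dose from 1 week prior to the" first screening visit, and on through Baseline.
- **Reason for the limit.** Protocol 3.2.1.2 gives safety first: it regards "elevating serum urate among those already in the upper range of normal at 7-8 mg/dL to clearly hyperuricemic levels above 8 mg/dL" as a risk not worth taking.
- **Who sees the results.** Protocol 7.2.2: "Beginning with the Baseline Visit, serum urate test results will not be provided to sites".
- **As-treated rule.** SAP 6.2 says of placebo participants that those "whose serum urate during treatment averages 6.5 mg/dL or greater will be reclassified as inosine participants".

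**The concern.** A drug look-back should protect the measurement that the drug can distort. Criterion 14 does so for the DAT scan and criterion 15 for the SC1 urate. Criterion 13 covers the drugs that lower urate most directly, yet it protects Baseline, where urate decides nothing about entry. As written, the washout can be done after the qualifying sample.

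Three things are at stake:

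- **Eligibility.** Someone whose own urate is near or within 7-8 mg/dL could be enrolled, against the stated purpose of the limit.
- **Initial dosage plan.** Protocol 5.1.2.2 derives it partly from screening urate and reports that higher screening values went with larger rises for a given dose. A falsely low value therefore misinforms the plan.
- **As-treated classification.** A placebo participant whose own urate averages 6.5 mg/dL or more would be moved to inosine while fully compliant. SAP 6.2 restricts that sample to eligible participants, but this person breaks no criterion and so stays in it.

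**Working it through.** The plan states no figure for this point, so the check is a day count, then the size of urate fall needed, then a bound on the effect.

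**1. Day count** (Baseline = day 0; criterion 13 covers day -30 onward, so the last permitted dose is on day -31; SC1 window from Protocol 7.7)

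| SC1 falls on | Permitted days | Share of 48 | Drug status at the qualifying draw |
|---|---|---|---|
| day -60 to -31 | 30 | 30/48 = 62.5% | may be taking the drug that day |
| day -30 to -13 | 18 | 18/48 = 37.5% | last dose at least 1 day (SC1 on -30) to 18 days (SC1 on -13) earlier |

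The longest uncovered interval is 60 - 30 = 30 days. The shares are of permitted calendar days, not of participants. Early SC1 dates are not a theoretical corner: the protocol's change summary records that 45 days had proved too short to schedule screening.

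**2. Would SC2 show it?** SC2 may precede day -30 on 28 of its 48 days (-58 to -31). In that case both screening values can be on-drug. Baseline is then the first off-drug measurement, and its result is withheld from the site.

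**3. Fall needed to qualify** = own urate - 5.7

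- own urate 6.5: 6.5 - 5.7 = 0.8 mg/dL
- own urate 7.0: 7.0 - 5.7 = 1.3 mg/dL
- own urate 8.0: 8.0 - 5.7 = 2.3 mg/dL

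For scale only, Protocol 2.2.2 (B2) cites a fall of 2 mg/dL with oxypurinol in heart failure. That is neither a listed drug nor this population. If a similar fall is assumed, any own urate up to 5.7 + 2.0 = 7.7 could qualify.

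**4. Bound on numbers.** The documents give no frequency. Assuming 0 to 2% of 270, 0.02 x 270 = 5.4, so 0 to 5 participants in all. With 1:1 allocation, 0 to about 3 would be on placebo and exposed to the 6.5 mg/dL rule.

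**5. Bound on the primary analysis.** The planned sample size reproduces. With slope difference 6.3/24 = 0.2625 per month, SD 0.758, two-sided alpha 0.046 and power 80%:

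n per arm = 2 x (1.995 + 0.842)^2 x (0.758/0.2625)^2 = 134.2, rounded up to 135, or 270 in total.

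As a pessimistic assumption, let a share of participants gain no effect at all. Power moves from 80.2% to 79.4% at a 1% share and 78.6% at 2%.

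**The case against.** **What stands**

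- The exclusions for gout and uric acid stones (criteria 3 and 4) remove many users of these drugs. The protocol's own background mentions their study in hypertension and heart failure, so the remainder is small but not empty.
- The site does see the SC2 urate and reviews it with the participant (Protocol 7.1.4). The medication log reaches back 30 days from SC2 (5.3.3), and urate-lowering drugs are banned during the study (5.3.2.2). An alert investigator may notice. None of these is an eligibility rule, though, and 5.3.2.1 refers pre-entry use back to section 4.2.
- Criterion 15 is an imperfect parallel, because thiazides may continue and only stability matters. Criterion 14 is the closer one.
- The 6.5 mg/dL rule is stated for the as-treated sample. The primary analysis uses the intent-to-treat sample, and the phase 2 trial had no such case among 25 placebo participants.

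**Stronger readings a reader might infer, which the documents do not support**

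- *That urate would reach 10 mg/dL or more*, by adding the planned 3 mg/dL rise to an own urate already above 7. The 3 mg/dL is the expected mean distance from 4.5 to a target of 7.5, reached by titration. It is not a fixed increment. Urate is checked at week 3, and values above 8.0 or 9.0 trigger the reduction and hold rules in 5.1.2.3.
- *That a falsely low titration baseline drives over-dosing.* In 5.1.2.3 the baseline enters only while urate is below 7.1, through (current - baseline)/(7.1 - baseline). Lowering the baseline raises that fraction, which points to the smaller step.
- *That inosine users are wrongly admitted.* Inosine raises urate, so its use at SC1 leads to a conservative screen failure.
- *That dopamine-blocking drugs open the same gap for the diagnosis.* Inclusion 2 requires the cardinal signs at Baseline as well as at SC2, drug-induced parkinsonism is excluded, and a DAT deficit is required.

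**Conclusion.** The gap follows from the text alone: the only urate limit is at SC1, SC1 may precede the look-back by up to 30 days, and no written criterion requires that sample to be free of allopurinol, febuxostat or probenecid. It allows a few participants whom the urate limit is meant to keep out. It also affects the initial dosage plan and, on placebo, as-treated classification.

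Severity is minor. The number affected is undocumented and probably very low; 0 to 5 of 270 is an assumption, and its range includes none. On-treatment titration limits exposure, and the intent-to-treat comparison is barely touched. A reader might go further and conclude that the enrolled population is not the low-urate population described. Without evidence on frequency, the documents do not support that.

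**What to change.** Take allopurinol, febuxostat and probenecid out of the shared Baseline window in criterion 13. Give them their own window, starting a stated time before SC1 and running through Baseline, in the pattern of criterion 15. The sponsor should set its length. The rest of criterion 13 can stay as it is. With this change, none of the 48 permitted SC1 days allows an on-drug qualifying sample. The cost is one line in section 4.2, a matching change to the electronic eligibility check, and a later SC1 for a few candidates.

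If enrolment is already complete, the amendment cannot help those participants. Before unblinding, list any participant whose medication log shows one of these drugs during screening, and report the as-treated analysis with and without reclassifying them under the 6.5 mg/dL rule. The log starts 30 days before SC2, so it may miss some use at an early SC1.
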